### 5.3.2. Immunogenicity Data

Any assays above LLOQ are considered accurate, and their quantitated values will be reported. Values below the LLOQ, or denoted as BLQ, will be set to  $0.5 \times \text{LLOQ}$  for analysis.

For calculating a fold rise,  $< \text{LLOQ}$  will be converted to  $0.5 \times \text{LLOQ}$  for a numerator, and  $< \text{LLOQ}$  will be converted to LLOQ for a denominator when only 1 of either the numerator or denominator is  $< \text{LLOQ}$ . If both the numerator and denominator are  $< \text{LLOQ}$ , then both will be converted in the same way.

The LLOQs for each assay will be included in the final released assay data.

Values for sera that are designated as QNS, indeterminate results, or values recorded as “not done” will be set to “missing.” Additionally, any time point with no blood draws will not be included in the analysis. No imputation will be done for these missing values, as MCAR is assumed for immunogenicity data according to Scott and Hsu.

## 6. ANALYSES AND SUMMARIES

### 6.1. Primary Endpoints

#### 6.1.1. Substudy A Primary Immunogenicity Endpoint

Participants will be summarized by vaccine group according to the study interventions to which they were randomized.

##### 6.1.1.1. Main Analysis

- Estimand strategy: Hypothetical approach ([Section 2.2.1.1](#)).
- Intercurrent events and missing data: All data collected after or at intercurrent events will not be included ([Section 2.2.1.1](#)); missing data will not be imputed ([Section 5.3.2](#)).
- Analysis set: Evaluable immunogenicity population ([Section 4](#)).
- Analysis timing: With the primary analysis when all primary endpoint data are cleaned for analysis.
- Analysis methodology:
  - Model-adjusted GMR, and the corresponding 95% CI of RSV A and RSV B NTs at 1 month after vaccination with RSVpreF of participants in Study C3671023 Substudy A ( $\geq 18$  to  $< 60$  years with high risk), compared to that of participants in the C3671013 efficacy study immunogenicity subset ( $\geq 60$  years), will be summarized along with sample size (n) and model-adjusted LS GMTs with the 95% CI for the corresponding group, using ANCOVA model ([Section 5.2.2.4](#)) that includes groups (Substudy A versus C3671013), corresponding baseline titers, and sex as covariates.
  - NT seroresponse rates at 1 month after vaccination will be summarized with the proportion (%) and the numerator (n) and denominator (N) for each group for RSV A and RSV B. The seroresponse rate difference between groups (Substudy A versus C3671013 immunogenicity subset) will be summarized with 95% CI using the Miettinen and Nurminen method for RSV A and RSV B ([Section 5.2.1](#)).
- RCDCs for RSV A and RSV B will be plotted 1 month after RSV vaccination, by age group.

##### 6.1.1.2. Supplementary Analysis

To support the assessment of immunogenicity, estimands, as specified in [Section 2.2.3](#) using the treatment policy strategy, may be summarized with the mITT immunogenicity population using the same presentation as specified in the main analysis, without the RCDCs.

### 6.1.1.3. Sensitivity Analysis

RSV A NTs and RSV B NTs at 1 month after RSVpreF vaccination will be summarized with unadjusted GMTs and GMFRs with the corresponding 95% CI ([Section 5.2.2.1](#) and [Section 5.2.2.3](#)) for the evaluable immunogenicity population.

### 6.1.2. Substudy B Primary Immunogenicity Endpoint

RSV A– and RSV B–neutralizing antibody titers will be summarized.

#### 6.1.2.1. Main Analysis

- Estimand strategy: Hypothetical approach ([Section 2.2.1.2](#)).
- Intercurrent events and missing data: All data collected after or at intercurrent events will not be included ([Section 2.2.1.2](#)); missing data will not be imputed ([Section 5.3.2](#)).
- Analysis set: Evaluable immunogenicity population ([Section 4](#)).
- Analysis timing: At the final analysis.
- Analysis methodology: 95% CIs of GMTs and GMFRs ([Section 5.2.2](#)).
- Descriptive statistics, including sample size (n), RSV A NT, RSV B NT, and RSV A/B NT GMTs and GMFRs, and 95% CIs for GMTs and GMFRs at each applicable visit, will be presented ([Section 5.2.2](#)) by age group ( $\geq 18$  to  $< 60$  and  $\geq 60$  years) as well as overall.
- RCDCs for RSV A and RSV B at each blood sampling time point will be plotted.

#### 6.1.2.2. Supplementary Analysis

To support the assessment of immunogenicity, estimands as specified in [Section 2.2.3](#), using the treatment policy strategy, may be summarized with the mITT immunogenicity population using the same presentation as specified in the main analysis, without the RCDCs.

### 6.1.3. Local Reactions and Systemic Events

Reactogenicity data ([Section 3.1.3.1](#) and [Section 3.1.3.2](#)) will be summarized separately for Substudy A and for Substudy B. Substudy A will be summarized for each of the 2 vaccine groups ([Section 2.2.1.3.1](#)).

For Substudy A, data will be summarized by vaccine group, according to the study interventions the participants actually received. For Substudy B, data will be summarized by age group ( $\geq 18$  to  $< 60$  and  $\geq 60$  years).

### 6.1.3.1. Main Analysis

- Estimand strategy: Treatment policy ([Section 2.2.1.3.1](#) and [Section 2.2.1.4.1](#)).
- Intercurrent events and missing data: All data collected are included; partially missing e-diary data are imputed from the AE CRF as “no” ([Section 5.3.1.1](#)); e-diary data that are confirmed as errors will not be used for analysis.
- Analysis set: e-diary safety population (only participants with at least 1-day of e-diary data transferred are included in the calculation) ([Section 4](#)).
- Analysis methodology: 95% CI of the proportion of participants reporting each event will be calculated using the Clopper-Pearson method ([Section 5.2.1](#)).
- Analysis timing: At primary analyses (when all primary endpoint data are available).
- Descriptive statistics, including the proportion (%), the numerator (n) and the denominator (N) used in the proportion calculation, and the 95% CI for percentage using the Clopper-Pearson method, will be presented for each group ([Section 5.2.1](#)).
- Bar charts with the proportions of participants for each and any local reaction and each and any systemic event throughout the 7 days will be plotted for each group. The bars will be divided into severity categories to highlight the proportions of participants by maximum severity.

### 6.1.3.2. Supplementary Analysis

To support the assessment of reactogenicity, the endpoints below, as specified in [Section 3.1.3.1](#) and [Section 3.1.3.2](#), will be summarized per the supplemental analysis with the same analysis population:

- Duration (days) of each local reaction and each systemic event after vaccination.
- Onset day of each local reaction and each systemic event after vaccination.

The presentation of the results will include a basic descriptive summary without the 95% CIs for each group.

### 6.1.3.3. Sensitivity Analysis

Two sensitivity analyses will be conducted:

- Maximum severity of reactogenicity is assessed for participants with all 7 days of e-diary data transmitted.
- Maximum severity of reactogenicity is also assessed using the e-diary data only. The difference between the primary analysis and this analysis will also be presented.

#### 6.1.4. AEs, SAEs, and NDCMCs

AEs, SAEs, and NDCMCs will be summarized, separately, for Substudy A and for Substudy B. Substudy A data will be summarized for each of the 2 vaccine groups ([Section 2.2.1.3.2](#), [Section 2.2.1.3.3](#), and [Section 2.2.1.3.4](#)).

For Substudy A, data will be summarized by vaccine group according to the study interventions the participants actually received.

##### 6.1.4.1. Main Analysis

- Estimand strategy: Treatment policy ([Section 2.2.1.3.2](#), [Section 2.2.1.3.3](#), [Section 2.2.1.3.4](#), [Section 2.2.1.4.2](#), [Section 2.2.1.4.3](#), and [Section 2.2.1.4.4](#)).
- Intercurrent events and missing data: All data collected are included.
- Analysis set: Safety population ([Section 4](#)).
- Analysis timing: At primary analyses (when all primary endpoint data are available).
- Analysis methodology: 95% CIs of the proportion of participants reporting those events will use the Clopper-Pearson method ([Section 5.2.1](#)).
- Descriptive statistics, including the proportion (%), the numerator (n) and the denominator (N) used in the proportion calculation, and the 95% CI for percentage using the Clopper-Pearson method, will be presented for each vaccine group for each analysis interval ([Section 5.2.1](#)).
- Bar charts with the proportions of participants for each variable within the specified interval will be plotted for each group. The bars may be divided into relatedness categories to highlight the proportions of participants with related events.
- The main analysis would be based on AEs excluding the reactogenicity events that were reported in the AE CRF (except for SAEs) ([Section 3.1.3.3](#)).

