### 2.2.1.3.2. AE Estimands

AE estimands have the same attributes (treatment condition, population, intercurrent events) as reactogenicity estimands ([Section 2.2.1.3.1](#)), except:

- **Variables:** Any AEs reported within 1 month after vaccination ([Section 3.1.3.3](#)).
- **Population-level summary:** The rates of reporting any AE within 1 month after vaccination.

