### 3.1.3. Primary Safety Endpoints for Substudy A and Substudy B

Primary safety endpoints include both reactogenicity data and AEs collected from the e-diary and AE CRF.

Based on feedback from the FDA on multiple vaccine programs, reactogenicity data will utilize both e-diary data (prompted local reactions and systemic events) and reactogenicity events reported in the AE CRF during the e-diary collection period. Since the AE CRF did not designate a specific page to collect reactogenicity data for an untransmitted e-diary, Pfizer has adopted a process of providing a listing of AEs reported within 7 days after vaccination to the clinical team to review and determine (“flag”) which PTs should be considered reactogenicity events before the database lock. AEs reported on the same day of vaccination but missing the AE start time are defaulted to AEs reported after vaccination.

Following these review steps, those AEs reported within 7 days after vaccination that match with those flagged PTs will be considered reactogenicity data. If the same reactogenicity events are reported on the same day from both the e-diary and the AE CRF, the highest grade from the 2 data sources will be used for that specific day for analysis.

It should be noted that the data collection in the AE CRF is different from that of the e-diary:

- For redness, swelling, and fever, the measured size of redness and swelling at the injection site and temperature are recorded in the e-diary, but not in the AE CRF. As the missing e-diary entries are monitored with ongoing review of the prompted reactions reported in the AE CRF, any measurement recorded in the query response will be taken into consideration for the primary analysis using the data handling memo for analysis purposes. For the 7 days, only the maximum grading from both sources will be used for the aggregated severity analysis.
- For pain at the injection site and all other systemic events, the severity grading algorithm for the e-diary data and the AE CRF may not be the same, though Pfizer will choose the highest-severity grade.

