If a participant did not have any e-diary data transferred within 7 days after vaccination, the AE CRF data in general will not be used for derivation, because this may inflate the denominator and bias the analysis, since participants who did not transfer e-diary data may be less likely to report reactogenicity. If a participant did not report any e-diary data, the participant will not be included in the analysis of reactogenicity data.

The subsections below describe how to derive each safety endpoint. Since the derivation is similar between Substudy A and Substudy B, no separate subsection is needed for each substudy.

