### **3.1.3.3. Adverse Events and Serious Adverse Events**

Standard algorithms for handling missing AE dates and missing AE severity will be applied as described in the Pfizer vaccine data standard rules. Completely missing AE start dates will not be imputed.

The following derivations will be included for each participant:

1. Any AE reported through 1 month after the last vaccination – If the AE started on the same day of the first vaccination, and if the AE start time is before the vaccination time, this AE would not be counted. Otherwise, if the AE start time is missing or after the vaccination time, the AE is included. Any AE reported 1 month after the last vaccination will not be included in the analysis.
2. Any related AE reported through 1 month after the last vaccination – Similar to the above except only a related AE is included (but excluding related reactogenicity reported within 7 days after vaccination).
3. Any immediate AE (AE start time is within 30 minutes after vaccination) reported after each (and any, if applicable) vaccination – Only include AEs that started on the same day of the vaccination and with nonmissing AE start time that is within 30 minutes of the vaccination. If the immediate AE is a related reactogenicity event, this would not be included as an immediate AE.
4. Any severe or life-threatening AE reported through 1 month after the last vaccination.
5. Any AE leading to study withdrawal after vaccination.
6. Any NDCMC reported throughout the study.
7. Any SAE reported throughout the study (including reactogenicity reported in the AE CRF during the e-diary collection period).
8. Any AESI reported throughout the study.

Any AE reported before the first vaccination will not be included in the derivation.

Variables 1 through 5 listed above will be derived with 2 approaches: excluding any reactogenicity (but not excluding reactogenicity SAEs) reported in the AE CRF during the e-diary collection period, and with no exclusion at all.

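### Nonserious reactions on the AE CRF from participants with no transmitted e-diary are in neither the main AE result nor the main reactogenicity result

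*SAP*

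**What the plan says.** **Main AE result.** SAP 6.1.4.1 uses the safety population and states: "The main analysis would be based on AEs excluding the reactogenicity events that were reported in the AE CRF (except for SAEs". SAP 3.1.3.3 gives the derivation. Variables 1 to 5 (any AE, related, immediate, severe or life-threatening, leading to withdrawal) are each produced twice: once "excluding any reactogenicity (but not excluding reactogenicity SAEs) reported in the AE CRF during the e-diary collection period", and once with nothing removed. SAP 3.1.3 decides which records count as reactogenicity: "those AEs reported within 7 days after vaccination that match with those flagged PTs will be considered reactogenicity data". None of these rules depends on whether diary data arrived.

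**Main reactogenicity result.** SAP 6.1.3.1 uses the e-diary safety population. SAP 4 defines it by one or more transmitted diary days, separately for Dose 1 and Dose 2 in Substudy B. For a participant with no diary data after vaccination, SAP 3.1.3 says that "the AE CRF data in general will not be used for derivation", and then: "If a participant did not report any e-diary data, the participant will not be included in the analysis of reactogenicity data". SAP 5.3.1.1 and Protocol 9.3.1 let CRF reactions fill gaps only where one to six diary days exist.

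**Related text.** SAP 6.1.4.3 commits to a sensitivity analysis on all AEs, with CRF reactogenicity included. Inside SAP 3.1.3.3, item 2 (related AEs) carries its own limit, "but excluding related reactogenicity reported within 7 days after vaccination". Item 3 (immediate AEs) carries another: "If the immediate AE is a related reactogenicity event, this would not be included as an immediate AE".

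**The concern.** The exclusion keeps one reaction from appearing in two main tables. That is reasonable where the reaction is counted in the reactogenicity table. The two main results use different analysis sets, however, and the exclusion is applied to the larger one without checking membership of the smaller one. For a participant with no diary, the exclusion does not move the reaction to the other table; it leaves it in no main table.

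A reader who takes the two main tables together would expect every reported event to be in one of them. Because the exclusion covers all of variables 1 to 5, a nonserious severe reaction, or one leading to withdrawal, drops out of its main row in the same way. SAEs are kept, and AESIs and NDCMCs are outside the rule.

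**Working it through.** The plan states no figure on this point, so there is none to reproduce. The check is a trace of the rules, followed by simple scaling.

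**1. Trace.** Take a flagged reaction on the AE CRF within 7 days of vaccination.

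| Diary days transmitted | Event | Main reactogenicity | Main AE | All-AE sensitivity |
|---|---|---|---|---|
| 1 to 7 | nonserious | counted | excluded | counted |
| 0 | nonserious | participant not in the set | event excluded, participant in denominator | counted |
| 0 | serious | participant not in the set | counted | counted |

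The second row is the gap. The two reactogenicity sensitivity analyses in SAP 6.1.3.3 do not close it: one needs all 7 diary days and the other uses diary data only.

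**2. Can such records arise?** Protocol 8.3.4 sends two kinds of reaction to the AE page whatever happens to the diary later: those in the first 30 minutes, and those reported to the site in place of a missed diary day. Against that, SAP 3.1.3 notes that people without diary data may be less likely to report reactions, and SAP 4 allows that the e-diary and safety populations may coincide. The number may be small or zero.

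**3. Substudy B.** In the per-dose tables, a participant with a Dose 1 diary and no Dose 2 diary is outside the Dose 2 set, so a Dose 2 reaction on the CRF has the same gap. For the any-dose variables the text does not settle the matter. SAP 4 spells out sets for Dose 1 and Dose 2 and none for any dose. SAP 3.1.3.1 brings CRF reactions into the derivation, while SAP 3.1.3 generally withholds them when no diary data followed the vaccination.

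**4. Size.** Planned group sizes from Protocol 10.7.9.5 and Table 1: 675 × 2/3 = 450 RSVpreF, 675/3 = 225 placebo, and 200 in Substudy B. One participant whose only AE is such a reaction moves the any-AE proportion by

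- 100/450 = 0.22 points (Substudy A RSVpreF)
- 100/225 = 0.44 points (Substudy A placebo)
- 100/200 = 0.5 points (Substudy B)

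In general the shift is d × r, where d is the share with no diary and r is the share of those whose only AE is a flagged CRF reaction. Neither is in the documents. With assumed values:

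- d = 1%, r = 5%: 0.01 × 0.05 = 0.05 points
- d = 5%, r = 30%: 0.05 × 0.30 = 1.5 points
- d = 10%, r = 50%: 0.10 × 0.50 = 5.0 points

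The spread reflects the assumptions, and nothing in the documents narrows it.

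**5. Items 2 and 3.** SAP 3.1.3.3 requires a version of variables 2 and 3 with nothing removed. The definitions of those two variables already remove related reactogenicity. Followed literally, related reactions, including those in the first 30 minutes, stay out of the version meant to include them. A programmer cannot satisfy both instructions.

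**The case against.** The strongest reply is that the SAP rule is uniform and reasoned. SAP 6.1.4.1 openly makes the main AE variable one of events other than reactogenicity. On that definition a participant with only a reaction has no such event, and the proportion is not wrong. Keeping no-diary CRF data out of the reactogenicity rates is justified in SAP 3.1.3, because it could inflate that denominator and bias the rate. A committed analysis of all AEs reports the events, and SAP 3.4.3 and 6.5.2 already report diary completion. Making the AE definition depend on diary status would count the same reaction as an AE in one person and not in another.

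Much of this stands, and it is why the point is minor. It does not close the gap. The denominator argument concerns the reactogenicity rates; in the AE result these participants are already in the denominator. The sensitivity analysis adds CRF reactogenicity for everyone, so it does not show which events were in no main table.

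Two stronger readings are tempting and should not be drawn.

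- A reader might infer a breach of the Substudy A AE estimand, summarized in SAP 2.2.1.3.2 as "The rates of reporting any AE within 1 month after vaccination". That argument would apply equally to the exclusion for participants with a diary, which is reasonable and which the fix leaves in place. It does not identify this gap.
- A reader might infer a biased RSVpreF-minus-placebo difference in overall AEs. No such difference is planned: Protocol 10.7.9.3.2 and SAP 6.6.1 give differences only for Tier 1 and Tier 2 events, and SAP 6.1.4.1 gives proportions by group.

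**Conclusion.** The gap is real and minor. It is confined to nonserious flagged reactions on the AE CRF, for participants with no transmitted e-diary and, in the Substudy B per-dose tables, for doses with none. The conclusion rests on the text of the rules and needs no assumption. The Substudy B any-dose results remain an open question.

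The amount cannot be found from the documents. Only the shift per affected participant is firm, and it assumes the planned group sizes. The safety analysis is descriptive, the any-AE count is recovered in the all-AE sensitivity analysis, and no study conclusion is threatened. The documents do not support saying that these events go unreported; they support only that the events are missing from the main results. The wording conflict in items 2 and 3 is a separate drafting fault, but it matters here because it weakens the recovery of related and immediate reactions.

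**What to change.** 1. In SAP 3.1.3.3 and 6.1.4.1, apply the reactogenicity exclusion only to participants in the e-diary safety population and, for Substudy B per-dose results, only to doses in it. Footnote the main AE table with the number of no-diary participants per group who contribute flagged events. If a uniform AE definition is preferred, keep the exclusion as written and show these participants and events by group as a separate row in the main AE table.
2. In SAP 3.1.3.3, state that the exclusions written into items 2 and 3 apply only to the with-exclusion derivation, so that the other version includes related and immediate reactions.

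The cost is SAP wording and one extra derivation condition (or one table row), settled before unblinding. Under the first option the AE percentages may rise slightly and the AE definition depends on diary status; the footnote shows how often, and SAP 6.1.4.3 stays as the uniform check. The separate row avoids that dependence. No new count of participants without a diary is needed, because the planned completion summary gives it.

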##### 6.1.4.2. Supplementary Analysis

To support the assessment of AEs, the endpoints below, as specified in [Section 3.1.3.3](#), will be summarized with the same analysis population using the same presentation as specified in the main analysis:

- Immediate AEs after each (and any, if applicable) vaccination
- Related AEs reported through 1 month after the last vaccination
- Severe or life-threatening AEs reported through 1 month after the last vaccination
- AEs leading to withdrawal from vaccination throughout the study

- NDCMCs reported from vaccination throughout the study
- AESIs reported from vaccination throughout the study

#### **6.1.4.3. Sensitivity Analysis**

In addition, a sensitivity analysis will be conducted by using all AEs (including reactogenicity reported in the AE CRF during the e-diary collection period).

